- 8) Review of medical conditions: *Must not have any medical conditions affecting IV ketamine safety or tolerability or that would interfere with participation in a long-term study. (i.e., life expectancy < 1 year because of terminal illness, unstable angina). Must not have inadequately controlled hypertension.*

D. Schedule of Measures

SCHEDULE OF MEASURES				FOLLOW – UP +++		
	BASELINE	ACUTE END (WK 4)*	CONTINUATION END (WK 8)**	1 MONTH	2 MONTH	3 MONTH
Screening						
SCID-5+	X					
PHQ-9	X			X	X	X
ATHF	X					

Short Blessed Test	X					
Blood Pressure	X					
AUDIT	X					
DAST	X					
CIRS-G	X					
Outcomes						
MADRS	X	X	X	X	X	X
Scale for Suicidal Ideation (SSI)	X	X	X			
Psychological well-being (NIH Toolbox)	X	X	X			
Cognitive Battery (NIH Toolbox)	X	X	X			
Miro Health Cognitive Battery	X	X	X			
Pittsburgh Sleep Quality Index (PSQI)++	X	X	X			
Safety						
AE Monitoring	X	X	X			
Medication List	X	X	X			
Medical History	X					
Height/Weight	X		weight			
ECG	X		X			
Blood Chemistries***	X		X			
Craving Scale	X	X	X			
Depression daily self-reports	THROUGHOUT					

*Acute End assessments will take place after at least 4 weeks of treatment or upon early termination from Acute phase. There may be some delays between baseline assessments and the start of treatment.

**Continuation End assessments will take place after the 8th week of treatment or upon early termination from Continuation phase.

*** Blood chemistries may include CBC, BMP (including LFTs); and TSH at baseline if not obtained within the last 6 months.

+Subset of SCID-5 will be administered to assess Bipolar And Related Disorders, Depressive Disorders, Schizophrenia And Other Psychotic Disorders

++Item 6 of PSQI will be administered.

+++ Follow-Up assessments (typically phone) will be conducted for participants who begin Continuation Phase at 1, 2, and 3 months after their last study visit (Wk 8, or their last study visit if the participant ends early)

E. Determination of Remission

1. Acute Phase End

Participants who complete the acute phase and reach a MADRS score indicating remission (<10) or response (30% reduction) will continue IV ketamine for 4 weeks. This continuation phase is needed to establish the stability of remission/response.

Participants without a 30% reduction in MADRS score at the end of the acute phase will not proceed to the Continuation Phase of the study; their participation will end.

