Vital Signs: Blood Pressure, Pulse rate, oxygen saturation, body temperature	X	X	X	X
Brief Psychiatric Rating Scale - positive (psychotic) symptom subscale (BPRS+)	X	X	-	X
Clinician Administered Dissociative States Scale (CADSS)	X	X	-	X

G. Potential Risks & Risk Mitigation

Interviews/Questionnaires/Surveys:

Participants may experience emotional discomfort with the neuropsychological testing and medical and psychological questionnaires. If any particular question makes the participant uncomfortable, the participant may discuss its importance and the need to answer it with the specially-trained interviewer. These assessments will be administered in private settings. Participants have the right to refuse to answer any question for any reason.

Infusion Procedure/Blood Draws/ Injections:

While rare, participants may experience pain, bruising, and/or bleeding at the site of needle insertion for blood draws, injections and the intravenous catheter. There is a rare risk of infection from a needle insertion. Phlebotomy, IM injection, and IV insertion will be performed by certified and trained staff.

Ketamine:

Common side effects: Feeling light-headed, “high,” exhilarated, having perceptual changes or hallucinations, floating sensations, and/or difficulty concentrating, paying attention, or remembering as many items as usual from a list (like items on a grocery list) Mild and temporary increases in blood pressure.

Less likely: Feeling dizzy, sleepy, anxious, suspicious, nauseated.

Rare side effects: Feeling sad, scared, confused, disoriented, moderate and temporary increases in blood pressure, future abuse of ketamine, prolonged psychosis in individuals with a pre-existing psychiatric condition. It is possible that the use of ketamine could increase interest in the illicit use or abuse of this substance although the fact that individuals with any past or current substance abuse will be excluded makes this highly unlikely.

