Safety will be systematically monitored during infusions according to the Safety Monitoring for Infusions schedule.

In addition, we will ask each participant to notify us of new symptoms, illnesses, or other problems.

B. Definitions of Adverse Events

An Adverse Event (AE) is any untoward medical occurrence in a subject or clinical investigation subject administered a drug under study. An AE does not necessarily have a causal relationship with the study drug.

The criteria for identifying AEs are:

- Any unfavorable and unintended sign (including an abnormal laboratory finding), symptom, or disease temporally associated with the use of a drug under study, whether or not considered related to the drug under study
- Any new disease or exacerbation of an existing disease

- Any deterioration in nonprotocol required measurements of a laboratory value or other clinical test (e.g., ECG or x ray) that results in symptoms, a change in treatment, or discontinuation of study drug
- Recurrence of an intermittent medical condition (e.g., headache) not present pretreatment (i.e., baseline)
- An abnormal laboratory test result should be considered an AE if the identified laboratory abnormality leads to any type of intervention, whether prescribed in the protocol or not.
- A laboratory result should be considered by the investigator to be an AE if it:
 - Results in the withdrawal of study drug
 - Results in withholding of study drug pending some investigational outcome
 - Results in an intervention, based on medical evaluation (e.g., potassium supplement for hypokalemia)
 - Results in any out of range laboratory value that in the investigator's judgment fulfills the definitions of an AE with regard to the subject's medical profile.

All AEs observed during the study will be reported on the Redcap AE form. All AEs, regardless of relationship to study drug or procedure, should be collected beginning from the time the subject signs the study ICF through the last visit.

Abnormal laboratory values should not be listed as separate AEs if they are considered to be part of the clinical syndrome that is being reported as an AE. Any laboratory abnormality considered to constitute an AE should be reported as an AE on the E-CRF.

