4. Assessing Seriousness of Adverse Events

A **Serious Adverse Event (SAE)** is any untoward medical occurrence that at any dose:

- Results in death
- Is life-threatening (i.e., the subject was at immediate risk of death from the adverse event as it occurred; this does not include an event that, had it occurred in a more severe form or was allowed to continue, might have caused death)
- Requires inpatient hospitalization or prolongation of existing hospitalization
- Results in persistent or significant disability or incapacity
- Is a congenital anomaly or birth defect in the child of a subject who was exposed to the study drug

Other important medical events that may not be immediately life threatening or result in death or hospitalization but, when based on appropriate medical judgment, may jeopardize the subject or may require intervention to prevent one of the outcomes in the definition of SAE listed above should also be considered SAEs. Medical and scientific judgment should be exercised in deciding whether expedited reporting is appropriate in such situations.

The following hospitalizations are not considered to be SAEs because there is no “adverse event” (i.e., there is no untoward medical occurrence) associated with the hospitalization:

- Hospitalizations for respite care
- Hospitalization planned before informed consent where the condition requiring the hospitalization has not changed post study drug administration
- Hospitalization for routine maintenance of a device (e.g., battery replacement) that was in place before study entry

D. Data Collection Procedures for Adverse Events

Participating sites are responsible for gathering and documenting data pertinent to Adverse Events occurring at their sites and for collecting Adverse Event information from each treating physician, including but not limited to:

- Description of the event, including onset and duration
- Treatment assignment, dose recommendation, and adherence
- Relevant medical and laboratory findings and reports
- Correspondence regarding the event
- Action taken in response to the event
- Classification of the Adverse Event (Severity, Relationship, Expectedness, Seriousness)

All Adverse Events observed during the study will be recorded on the Redcap AE form. All Adverse Events will be collected from the time of informed consent through the last assessment.

1.a Reporting Procedures for Adverse Events

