2.2. Objectives

2.2.1. Objectives and study aims

The study aims to learn whether it is feasible to conduct a larger, longer trial in the future to learn about the long-term effects of ketamine infusions. In addition, this study will develop and utilize innovative methodological approaches to demonstrate the feasibility of precision medicine and mHealth approaches in depression treatment.

The study will also provide preliminary data on response and remission rates, adverse events, and cognitive changes with ketamine during a 4-week acute phase, 4-week continuation phase, and 3-month post-infusion follow-up phase.

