2.2.2. Hypothesis

Ketamine infusions will show preliminary evidence of acute and continuation efficacy, as assessed by response and remission rates, and changes in MADRS score.

Ketamine infusions will be safe and well-tolerated as measured by adverse events (AEs) and severe adverse events (SAEs).

Ketamine infusions will produce increases in cognitive function as measured by NIH Toolbox and Miro measures.

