5.5. Safety and Adverse Events

5.5.1. Safety Monitoring

Safety will be systematically monitored during infusions according to the Safety Monitoring for Infusions schedule. In addition, we will ask each participant to notify us of new symptoms, illnesses, or other problems.

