5.5.2. Recording Adverse Events

During the study, regular assessments for AEs will be conducted and recorded in REDCap. Participating sites are responsible for gathering and documenting data pertinent to AEs occurring at their sites and for collecting AE information, including but not limited to:

- a) Description of the event, including onset and duration.
- b) Doses of study medications and adherence.
- c) Relevant medical and laboratory findings and reports.
- d) Correspondence regarding the event.
- e) Action taken in response to the event.
- f) Classification of the AE (Severity, Relationship, Expectedness, Seriousness).

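### The SAP promises adverse-event data through the 3-month follow-up, but no adverse-event query is scheduled at the follow-up calls and the protocol gives two different end points for collection.

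*SAP*

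**What the plan says.** SAP 2.2.1 lists the preliminary data the pilot will provide. Besides response and remission rates, it names "adverse events, and cognitive changes with ketamine during a 4-week acute phase, 4-week continuation phase, and 3-month post-infusion follow-up phase". SAP 2.2.2 makes safety and tolerability, measured by AEs and SAEs, one of the study hypotheses.

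The follow-up contacts are defined in footnote +++ to the Schedule of Measures (Protocol II.D): "Follow-Up assessments (typically phone) will be conducted for participants who begin Continuation Phase at 1, 2, and 3 months after their last study visit". The footnote identifies that last visit as Week 8, or an earlier one if the participant ends early. In the schedule, AE Monitoring is marked at baseline, Week 4 and Week 8 only. At months 1, 2 and 3 the marked measures are MADRS and PHQ-9. SAP 3.1 likewise places safety assessment at baseline, end of acute phase and end of continuation.

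The protocol states the end of AE collection twice:
- Section III.B says AEs "should be collected beginning from the time the subject signs the study ICF through the last visit".
- Section III.D says "All Adverse Events will be collected from the time of informed consent through the last assessment".

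On method, Protocol III.A and SAP 5.5.1 describe monitoring during infusions and add that "we will ask each participant to notify us of new symptoms, illnesses, or other problems". SAP 5.5.2 adds: "During the study, regular assessments for AEs will be conducted and recorded in REDCap". It names neither visits nor an end date.

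**The concern.** The SAP includes adverse events in what it will report for follow-up, but the schedule gives staff no prompt to ask about them then. Infusion monitoring stops with the last infusion. What remains is the participant's own report and an assessment described only as regular. Because the end of collection can be read two ways, sites following different sentences in good faith could stop about three months apart.

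This matters because safety is a main aim of the pilot, and its results are meant to inform a larger, longer trial. The protocol's list of rare ketamine effects (II.G) includes "future abuse of ketamine, prolonged psychosis in individuals with a pre-existing psychiatric condition". Both could appear or persist after the last infusion, so follow-up is where they would be seen. The Craving Scale also stops at Week 8. A low or zero AE rate in follow-up could then reflect how events were collected rather than how safe the treatment was.

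**Working it through.** The plan states no figure to reproduce. The check is a comparison of the texts, followed by arithmetic for scale.

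**1. Schedule against the SAP aim**

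| Item | Baseline | Wk 4 | Wk 8 | Months 1, 2, 3 |
|---|---|---|---|---|
| AE Monitoring | yes | yes | yes | 0 of 3 |
| MADRS | yes | yes | yes | 3 of 3 |
| PHQ-9 | yes | no | no | 3 of 3 |
| AE data per SAP 2.2.1 | n/a | acute phase | continuation phase | included |

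The MADRS and PHQ-9 rows are intact in the text, so the missing AE marks are unlikely to be an extraction fault. The AE row is not a full list of safety checks, since infusion visits have their own safety table. But no other table or sentence places a safety query at the calls.

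**2. End of collection**
- III.B stops at the last visit. The footnote uses last study visit for Week 8 or early end, so III.B points to Week 8.
- III.D stops at the last assessment. The footnote calls the later calls follow-up assessments, so III.D points to month 3.
- Nothing in either document resolves the difference.

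**3. Time affected** (3 months taken as about 13 weeks, an assumption)
- A participant who completes continuation is observed for 8 + 13 = 21 weeks. The share after the last scheduled AE query is 13/21 = 62%.
- Each phase may be extended by 4 weeks. With both extended, the share is 13/(16 + 13) = 13/29 = 45%.

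**4. People affected** (assumption: 50% to 80% begin continuation)
- SAP sample of 25: 25 × 0.5 = 12.5, rounded to 13, up to 25 × 0.8 = 20. Calls: 3 × 13 = 39 to 3 × 20 = 60.
- Protocol sample of 15: 15 × 0.5 = 7.5, rounded to 8, up to 15 × 0.8 = 12. Calls: 24 to 36.

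**5. What a recorded zero would mean**

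With zero events in n people, the exact two-sided 95% upper limit is U = 1 − 0.025^(1/n). If only a fraction c of affected people is captured, the recorded proportion estimates c × p. The limit for the true proportion p is then U/c. The values of c below 1 are assumptions; the documents give none.

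| Capture c | n = 13 | n = 20 |
|---|---|---|
| 1.0 | 24.7% | 16.8% |
| 0.8 | 30.9% | 21.1% |
| 0.5 | 49.4% | 33.7% |

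**6. Two smaller inconsistencies**
- SAP 2.2.1 also places cognitive change in follow-up, but no battery is scheduled after Week 8 and SAP 5.1.2 defines cognitive change at Weeks 4 and 8 only.
- The suicide-risk text in Protocol II.G states formal assessment at least every two weeks throughout the study. If that includes follow-up, the contacts are only monthly.

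**The case against.** The best reply is that SAP 2.2.1 is a loose summary joining several data types to several phases. It cannot mean every type in every phase, as the cognitive item shows. SAP 3.1 is more specific, agrees with the schedule and ends scheduled safety assessment with continuation. On that reading only the wording of 2.2.1 is at fault, and narrowing it to Week 8 would restore consistency. This stands as an alternative remedy. But SAP 3.1 confirms that 2.2.1 and the schedule disagree, and it does not settle when AE collection closes.

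Second, III.D is the data-collection section. Read with the footnote, it takes the window to month 3, so the conflict may come down to one loose word in III.B. Even so, that reading sets a window without giving staff a query to fill it.

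Third, the stakes are limited:
- Psychotic-spectrum disorders, bipolar disorder and current substance use disorders are excluded.
- Participants must be free of symptoms before each discharge.
- The protocol considers ketamine abuse highly unlikely.
- Staff speak to participants at every follow-up contact, and the suicide-risk algorithm applies if triggered.
- Analyses are descriptive, and without a control arm late events would be hard to attribute.

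All of this lowers the stakes. None of it is a general AE query.

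Finally, the percentages in step 5 depend on assumed continuation and capture rates. That is correct. They illustrate scale; the documented facts are the missing marks and the two end points.

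**Conclusion.** The concern holds. The text of the documents alone shows that AE Monitoring is marked at 0 of 3 follow-up contacts while SAP 2.2.1 includes follow-up AE data, and that III.B and III.D can be read as ending collection about 13 weeks apart. Collection in follow-up is not barred, and staff may ask informally, so the defect is in scheduled ascertainment and in the stated window. It applies only to participants who begin continuation, and the Week 4 primary outcome is untouched. The likely result is uneven follow-up AE data that cannot support a statement of safety in that period. How uneven cannot be known from the documents. This should be corrected, though it does not threaten the pilot as a whole.

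**What to change.** Mark a solicited AE and SAE query at the month 1, 2 and 3 contacts in the Schedule of Measures. Reword Protocol III.B and III.D so that both close AE collection at the last follow-up contact or, for participants who do not begin continuation, at their last study visit. In SAP 5.5.2, state that the regular assessments include these contacts.

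In the same amendment, remove cognitive change from the follow-up part of SAP 2.2.1, and make the two-weekly statement in the suicide-risk text agree with the monthly follow-up contacts.

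The cost is a few minutes on each call already planned (39 to 60 calls under the assumptions above with 25 participants), three marks in the schedule, wording edits, IRB approval of the change and notice to the sites. No new visits are needed.

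If the sponsor does not want AE data from follow-up, the minimum is to limit SAP 2.2.1 to the end of continuation and still give III.B and III.D one end point. That restores consistency but gives up safety information that the calls could supply at little cost.

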2.2.2. Hypothesis

Ketamine infusions will show preliminary evidence of acute and continuation efficacy, as assessed by response and remission rates, and changes in MADRS score.

Ketamine infusions will be safe and well-tolerated as measured by adverse events (AEs) and severe adverse events (SAEs).

Ketamine infusions will produce increases in cognitive function as measured by NIH Toolbox and Miro measures.

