2.2.3. Scope

This Statistical Analysis Plan will be the guiding document for the quantitative analyses that will be conducted in the Ketamine pilot study.

3. Study Methods

3.1. Study Design and Plan:

The study will enroll approximately 25 participants across 5 sites in the US and Canada.

Participants will receive ketamine infusions twice a week for 4 weeks (acute phase). At the end of the acute phase, those who have a MADRS score <10 or have a MADRS $\geq 30\%$ reduction from baseline will continue with an additional 4 weeks of weekly ketamine infusions (continuation phase). Participants whose MADRS score was not reduced at least 30% from baseline will not proceed to the Continuation Phase of the study; their participation will end. At the end of continuation phase, those who complete the Continuation phase will be assessed for remission and response using the MADRS.

Participants will be assessed at baseline, end of acute phase, and end of continuation phase for effectiveness, safety, and executive functioning. Participants will be asked to complete daily surveys of

their depression symptoms during their participation. Participants who choose to withdraw from the study early (during acute phase) will be treated as did not respond or remit. Final visit prior to withdrawing early from the study is not required.

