5.1.2. Outcome measurements

Change in Depression Severity as measured by MADRS at Week 4 and 8.

Change in Psychological Well-Being as measured by NIH Toolbox Psychological Well-Being Surveys, Positive Affect and General Life Satisfaction at Week 4 and 8.

Change in Cognition as measured by NIH Toolbox and Miro Health Cognitive Batteries at Week 4 and 8.

Change in Executive Function as measured by NIH Toolbox and Miro Health Cognitive Batteries at Week 4 and 8.

Change in Suicidal Ideation as measured by Scale for Suicidal Ideation at Week 4 and 8.

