5.2. Analysis methods

Data analysis will be mostly descriptive, including rates of response and remission and AEs.

Continuous changes in depressive symptoms and cognitive changes will also be measured with mixed-effect model.

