5.4. Interim analyses and stopping rules

No interim analysis is planned due to the nature of the trial. As there is no control arm and all treatments are FDA-approved and frequently used in older adults, no contingency plans for early stopping because of futility or safety are planned.

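### The SAP hypothesises that ketamine will raise cognition, but an uncontrolled repeat-test design with no provision for practice effects cannot attribute a rise to ketamine

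*SAP*

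**What the plan says.** SAP 2.2.2 lists three hypotheses. The efficacy one is hedged as preliminary evidence. The cognitive one is directional and causal, with no hedge: "Ketamine infusions will produce increases in cognitive function as measured by NIH Toolbox and Miro measures".

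The matching outcomes in SAP 5.1.2 are "Change in Cognition as measured by NIH Toolbox and Miro Health Cognitive Batteries at Week 4 and 8" and "Change in Executive Function as measured by NIH Toolbox and Miro Health Cognitive Batteries at Week 4 and 8". On analysis, SAP 5.2 says only: "Continuous changes in depressive symptoms and cognitive changes will also be measured with mixed-effect model".

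On design, SAP 3.1 says: "Participants will be assessed at baseline, end of acute phase, and end of continuation phase for effectiveness, safety, and executive functioning". The Protocol's Schedule of Measures (II.D) marks the NIH Toolbox cognitive battery and the "Miro Health Cognitive Battery" at those three visits and at no follow-up contact, so each has one scheduled administration before treatment. SAP 5.4 confirms the single arm when it explains why no stopping rule is planned: "As there is no control arm and all treatments are FDA-approved and frequently used in older adults".

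Participants who do not meet the MADRS continuation rule at the end of the acute phase leave the study (Protocol II.E, SAP 3.1). Week 8 scores therefore come only from those who entered continuation.

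In the text available, neither document mentions practice or learning effects, alternate forms, a run-in administration, practice-adjusted or reliable-change scores, or an external comparison.

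**The concern.** Scores on a cognitive battery can rise simply because the person has taken it before. Here every change score starts from the first scheduled exposure to the battery, and nobody is retested without ketamine. If the hypothesis is kept as worded, a before-after rise would be reported as something that ketamine produced.

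Practice is not the only rival. Mood may improve for any reason and lift test performance. Regression to the mean may also contribute, since participants enter on a high PHQ-9 score. Its direction on cognition is not certain, because the Short Blessed Test cut-off selects the other way.

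The problem runs in both directions: a practice gain can cancel a true decline, so a flat result is no more interpretable than a rise. At Week 8 there is a further difficulty, because change from baseline is then seen only in a group selected on MADRS.

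**Working it through.** **1. Can the planned data separate practice from drug?** The planned schedule gives:

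| Visit | Administration of each battery | Scheduled infusions so far |
|---|---|---|
| Baseline | 1st | 0 |
| Week 4 | 2nd | 2 × 4 = 8 |
| Week 8 (continuers only) | 3rd | 8 + 1 × 4 = 12 |

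Test exposure, ketamine exposure and time advance together. The expected change at Week 4 is practice + drug effect + other before-after change, which is one observable mean with at least three unknown parts. A mixed-effect model can estimate the sum. It cannot split it without a comparison group or outside information on practice, and SAP 5.2 names neither.

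**2. How large could the effect be?** The documents give no SD, effect size, alpha or success rule for cognition, so there is no planned figure to reproduce. What follows is an illustration.

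Inputs from the documents: n of about 25 (SAP 3.1) or up to 15 (Protocol II.B). The difference between these is a separate matter, so both are shown.

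Assumptions: ketamine effect zero; practice gain d of 0.1, 0.2 or 0.3 baseline SD; retest correlation r of 0.7 to 0.9; equal SDs at both visits; complete pairs. The yardstick, a 95% CI for mean change lying wholly above zero, is chosen here and is not an SAP rule.

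Formulae:
- SD of change = √(2(1 − r)) baseline SDs. At r = 0.8 this is √0.4 = 0.632.
- Standardised change dz = d / SD of change. At r = 0.8: 0.1/0.632 = 0.16, 0.2/0.632 = 0.32, 0.3/0.632 = 0.47.
- Probability = P(T > t₀.₉₇₅,ₙ₋₁), where T is noncentral t with n − 1 degrees of freedom and noncentrality dz√n.

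Results, per measure and per visit:

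| r | n | d = 0.1 | d = 0.2 | d = 0.3 |
|---|---|---|---|---|
| 0.7 | 15 | 6.8% | 15.2% | 28.7% |
| 0.7 | 25 | 9.0% | 23.6% | 46.0% |
| 0.8 | 15 | 8.3% | 20.7% | 40.2% |
| 0.8 | 25 | 11.5% | 32.9% | 62.4% |
| 0.9 | 15 | 12.5% | 36.5% | 67.6% |
| 0.9 | 25 | 18.8% | 57.4% | 89.6% |

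With no practice gain the probability is 2.5%. Every cell exceeds that, but only 4 of the 18 exceed 50%. Fewer complete pairs would lower the figures.

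**3. Masking.** If ketamine lowered a score by an assumed 0.2 SD and practice raised it by 0.2 SD, the expected change would be −0.2 + 0.2 = 0.

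**4. Week 8.** The Week 4 mean covers all participants with data, while the Week 8 mean covers continuers only. Setting one beside the other mixes change over time with change in who is measured. Within continuers, baseline-to-Week-8 change is the sum of the two interval changes, and these can be shown separately.

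**The case against.** The strongest reply is that this is a descriptive pilot. SAP 4.1 and 5.2 say so, SAP 2.2.1 calls the cognitive results preliminary, the outcome in SAP 5.1.2 is named simply as change, and the primary outcome is Week 4 remission. A single arm is defensible for feasibility, and the lack of attribution applies to MADRS change too. All of this stands, and it limits the point to wording and reporting. It does not remove the point: a confidence interval expresses sampling error, not bias, and the sentence in SAP 2.2.2 still assigns the change to ketamine.

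A reader might infer four stronger things that the documents do not support:

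- *That a positive cognitive result is likely even if ketamine does nothing.* Practice size and retest correlation are not documented, and most of the assumed grid lies below 50%. The documents support possible, not likely.
- *That the plan formally tests and would confirm the hypothesis.* There is no alpha, threshold or decision rule for cognition, so the 2.5% reference is not an error rate that the SAP claims.
- *That a false procognitive signal would be carried into the larger trial.* Protocol III.E makes a larger trial conditional on feasibility and a positive signal, but does not define that signal as cognitive.
- *That the plan's safety conclusion rests on these scores.* SAP 2.2.2 measures safety by adverse events, and the schedule lists both batteries under outcomes. Masking limits how the cognitive scores can be read. It is not shown to hide a harm that the safety analysis would miss.

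It is also fair that Protocol II.E and SAP 3.1 state openly who reaches Week 8. They do not say what that does to the cognitive change.

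**Conclusion.** The point holds as one of attribution. The hypothesis claims a causal effect on cognition that this design cannot show, and no analysis of the planned data alone can repair that. That conclusion follows from the schedule and the single arm and needs no assumed figure.

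The size of the problem does rest on assumptions. With r = 0.8 and no drug effect, practice gains of 0.1 to 0.3 SD put one measure's interval wholly above zero in 12% to 62% of trials of 25, or 8% to 40% of trials of 15. Across r of 0.7 to 0.9 the ranges are 9% to 90% and 7% to 68%. The true practice gain on these batteries in this population is not given in the documents, so no single cell should be read as the expected rate.

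**What to change.** Amend the SAP in three places:

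- **2.2.2:** replace the cognitive hypothesis with an estimation aim, for example: *to estimate within-person change in cognition, which includes practice effects and other before-after changes*.
- **5.1.2 or 5.2:** state that gains will not be attributed to ketamine, and that absence of decline will not be read as absence of harm.
- **5.2:** report baseline-to-Week-4 change in all analysed participants with data. In continuers, report baseline-to-Week-4 and Week-4-to-Week-8 changes separately, and say that Week 8 scores come only from those who met the continuation rule.

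The cost is a few sentences and one extra row in a results table, with no new data, visit or procedure. A control arm is not being asked for. Nor is a pre-treatment practice session: it would add testing to the Protocol schedule at every site, might not exhaust practice gains, and would leave mood improvement and regression to the mean untouched.
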